There are two standing committees that will provide organizational structure for this project, alongside an individual independent medical monitor. These are the Executive Committee and the Operations Committee.

Executive Committee: The Executive Committee has overall scientific and administrative responsibility for the conduct of the project. The Data Safety and Monitoring Board (DSMB) will report their recommendations to the Executive Committee where final decisions will be made. All changes or alterations to the protocol, or issues related to financing or administrative conduct of the study must be approved by the Executive Committee. The Executive Committee will also serve as the Publications Review Committee and all publicity, presentations, or manuscripts from the study must receive approval at this level. The Executive Committee will meet on a regular basis; the frequency will be decided based on the needs of the study. The specific members of the Executive Committee are not yet finalized.

Operations Committee: The Operations Committee will have primary responsibility for the implementation of the study protocol under the direction of the Executive Committee. They will develop and test all necessary study forms and procedures and produce a Manual of Operations that will document all procedures and methodology for the project. This committee will make recommendations to the Executive Committee regarding any proposed additions or alterations to the study protocol. The Operations Committee will meet on a regular basis; the frequency will be decided based on the needs of the study. The specific members of the Operations Committee are not yet finalized.

Data Safety and Monitoring Board: The purpose of the DSMB is to provide external, objective advice to the Executive Committee regarding the safety and efficacy of the interventions being evaluated. This committee will be responsible for reviewing the data from the study on a regular basis, summarizing their conclusions and advice in a written set of minutes, and communicating this information to the Executive Committee. The PI will then forward these minutes to the Institutional Review Boards at the University of Washington. The DSMB has specific responsibility to determine if there are problems relating to the safety of the intervention, to the degree the trial should be stopped, and to determine if the study should be stopped early because the benefit of the interventions has proved to be stronger than originally anticipated. The DSMB will meet just prior to the pre-season enrollment of shelter participants to review the final protocol, and once a year after the beginning of data collection to review accumulated data. Voting membership on the DSMB is limited to persons external to the investigative team. Senior members of the investigative team will serve as ex-officio members without voting rights. The specific composition of the DSMB will include expertise in biostatistics, epidemiology, and clinical infectious diseases. In addition to the voting members of the DSMB, study investigators will act as resources to the DSMB in a non-voting capacity.

As data accumulate, the DSMB will review whether there is enough evidence such that the continuation of the study would not yield any further meaningful data on treatment effects. While we do not believe *a priori* stopping rules are an appropriate approach to decision making in clinical trials (with the exception of evidence of spread for baloxavir antiviral resistance), we recognize that the DSMB may feel differently. If stopping rules are desired by the DSMB we will use those of O'Brien and Fleming. These rules use a conditional power framework and are commonly used in clinical trials.

Plan for reporting unanticipated problems/adverse events:

- **Serious Adverse Events:** Serious adverse events (SAEs) under Good Clinical Practice (GCP) guidelines include death, a life-threatening reaction to the study drug or other study procedure, hospitalization, or significant or persistent disability or impairment.
- **Other Adverse Events:** This will include any untoward medical event that occurs in a participant, any unfavorable sign or symptom disease temporally associated with the provision of the intervention, or any noxious or unintended response to the study drug. These other adverse events can be anticipated based on what we know about reactions to antiviral medications, or unanticipated. Examples of anticipated adverse events include (but are not limited to) instances of nausea, headache, or diarrhea. Unanticipated adverse events are those

that are either unexpected in terms of nature, severity, and frequency especially if they indicate that there is greater risk of harm than previously recognized.

On days 2/3 and 5/6/7 following receipt of the study drug, all study participants will be asked to complete questionnaires pertaining to evidence of short-term reaction during their interaction with the kiosk study staff, in addition to providing additional nasal swab specimen and daily symptom logs. A final questionnaire to assess for AEs and SAEs will be administered on Day 14. These questionnaires will be monitored daily by the data management team, such that adverse events will be reported in real-time.

All SAEs (regardless of causality), and any grade 3 and 4 AEs which are deemed related or possibly related to the study drug, will be logged in the AE database and reported electronically to the designated principal investigator ([name]) for review within 48 hours . This review will determine if there is any indication for the event being related to the study intervention or procedures. The clinical investigators will review the file and make a determination regarding attribution to study procedures or the intervention.

If the adverse event is considered by the clinical team to be minor in severity, it will be logged in the centralized data capture system and a summary of such events will be reported to the DSMB. If the severity of the adverse event is considered to be moderate or severe by Principal and Co-Principal Investigators, it should be reported to the safety officer (DSMB) and the cognizant IRB immediately. All study-related SAEs will be reported to the IRB within 14 days.

The following are a list of anticipated and unanticipated adverse events we expect to be attributable to the study procedures or the intervention:

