The trial is a stepped-wedge cluster-randomized design clustered by homeless shelter. The intervention is implementation of on-site point-of-care molecular influenza testing and treatment with a single dose of baloxavir or a 5-day course of oseltamivir for all influenza-positive cases. Homeless shelters will be randomized to begin the intervention at different times throughout flu season. Residents within shelters will be eligible to participate if they have acute cough or two or more qualifying ARI symptoms (See **Table 1** for symptom list). The

control condition is an influenza-surveillance kiosk installed in a shelter that allows participants to collect a nasal swab that is then sent to an outside lab for testing. During the intervention period, symptomatic individuals with symptom onset in the last 48 hours will be eligible for point-of-care testing at a “improved” kiosk with a molecular test for influenza and an antiviral intervention if they have not yet received antiviral treatment for their symptoms. If they test positive for influenza, they will be administered an antiviral (either baloxavir or oseltamivir) when they receive their results. All participants will receive active drug; there will be no placebo arm. During the intervention period, symptomatic individuals with symptom onset in the last 3-7 days will be eligible to participate in swab collection, but will not receive point-of-care testing or antiviral treatment. Whole genome sequencing of all influenza-positive samples detected will enable the study team to determine whether a participant has acquired and transmitted the pathogen to secondary cases within-shelter, or whether a case represents a community-acquired infection.

Figure 1. Trial intervention schema

[figure not shown]

Primary outcome measure of the trial is number of cases of influenza per person-day in the shelter during the intervention period compared to the control period.

Secondary outcomes:

- Symptom duration and severity among cases
- Viral titer and shedding duration among cases
- Feasibility of implementation
- Cost effectiveness
- Emergence of viral resistance

Figure 2. Stepped wedge design for trial

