The trial is being conducted in nine homeless shelters in the Seattle, WA metropolitan area. The aim is to enroll nine shelters, each with a nightly population of between approximately 45 to 212 individuals for a total number of a maximum 1,696 individuals under surveillance each influenza season. We will conduct this trial over two influenza seasons with re-randomization of the shelters each season for timing of the intervention. The University of Washington is the sponsor of the trial which is supported by an anonymous funder who does not have any ownership over the management and conduct of the study, the data, or the rights to publish.

III. Objectives

The objective of the trial is to evaluate the efficacy of on-site testing and rapid antiviral treatment with baloxavir or oseltamivir in influenza-positive individuals for prevention of secondary cases of influenza virus infection within homeless shelters.

Primary Outcome Measure

The primary outcome measure will be the incidence of cases of influenza in shelters during the intervention period compared to the incidence of cases during the control period. It will be calculated as the number of cases of laboratory-confirmed influenza among shelter residents divided by the number of unique shelter residents tested. The incidence during intervention periods will be compared to the incidence during non-intervention periods using a generalized linear mixed model to control for clustering, differences in shelters, and time period.

Secondary Outcome Measures

Feasibility and adherence outcomes

- Feasibility of implementation of point-of-care molecular testing and treatment of influenza in shelters (time between symptom onset until diagnosis)
- Feasibility of implementation of influenza treatment in shelters (time between symptom onset until treatment)
- Proportion of participants that become lost to follow-up (after testing positive for influenza at baseline enrollment and receiving an antiviral)
- Proportion of participants that show non-compliance with study drug (only applicable to oseltamivir)

Clinical outcomes

- Symptom type, duration and severity among viral positive cases (including broken down by influenza sub-type)
- Prevalence of asymptomatic and pauci-symptomatic influenza-positive cases
- Proportion of laboratory-confirmed influenza cases that report fever
- Relationship between symptom type, duration and severity, and current seasonal influenza vaccination status

Laboratory outcomes

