- Influenza viral RNA levels
- Proportion of samples with detectable influenza RNA virus at days 2/3 and days 5/6/7
- Proportion of cases in the shelter that are found via sequencing to be secondary cases, and proportion that are community-acquired
- Emergence of antiviral resistance, assessed by genetic sequencing of influenza strains

Hypothesis

Our primary hypothesis is that implementation of a point-of-care diagnostic and antiviral treatment intervention among sheltered individuals experiencing homelessness will reduce the incidence of influenza within this population over the course of an influenza season.

IV. Study Population

Participants will be any individuals staying at any of the shelters participating in the study. Participants ≥ 12 years of age who test positive for influenza will be given baloxavir as treatment and receive a 7-day follow-up from the study team. Participants < 12 years of age, women who are pregnant or breastfeeding, those with active malignancy, liver disease, and participants who are immunocompromised (see **Table 3**) who test positive for influenza will receive a 5-day course of oseltamivir. Based on an average of 164 specimens collected per month at two shelters over one influenza season during this study's pilot year, we anticipate that enrollment numbers at an additional 7 shelters will more than triple throughout each season (on average ≥ 492 specimens per month collected). This is due to the increased target population (412 to 1,032) and the increased number of hours/days spent conducting participant enrollment and specimen collection at each shelter proposed in this study design.

Sample size

The study aims to demonstrate a reduction in symptomatic influenza virus infections after implementation of point-of-care molecular testing for influenza and early treatment with baloxavir or oseltamivir. Power calculations were based on an assumed 1.67% incidence rate per month, which was determined based on assumed 12% incidence rate during the flu season. The table below outlines the power based on various estimated effect sizes and number of shelters-seasons (shelters x season):

		Power (%) to detect intervention effect as a function of RR and number of shelter-seasons. Assumptions: Six month flu season, average shelter census = 200, effective control incidence rate = 1.6%/month (=2%*.8), SD(shelter) = .0028, SD(shelter*month) = .0032, SD(intervention) = 0.					
		Number of shelter-seasons					
		8	12	16	18	24	32

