RR	.7	21	31	36	41	51	63
	.65	27	40	48	54	65	77
	.6	34	51	60	67	77	88
	.5	52	72	81	86	93	98

Assuming nine shelters participating for two seasons each (18 shelter-seasons), we would have an estimated 86 percent power to detect a risk ratio of 0.50 at a 0.05 two-sided significance

level, and assuming 200 participants per shelter. The incidence during intervention periods will be compared to the incidence during non-intervention periods using general estimating equation models to control for clustering, differences in shelters, and time period. Power calculation details can be found in **Additional File 2**.

Individual enrollment criteria

Participants must fulfill all of the following inclusion criteria:

- Resident for 1 or more days at a participating shelter
- 3 months or older
- Acute cough or ≥ 2 ARI symptoms (see **Table 1** for list)
- Willing to take study medication
- Willing to comply with all study procedures, including weekly surveillance and repeat nasal swab at day 2/3 and day 5/6/7 post-treatment.
- Able to provide written, informed consent and/or assent

Table 1 – ARI trigger symptoms (participants should have ≥ 2 or more of the following new symptoms for eligibility within the past 7 days during the control period and within the past 48 hours during the intervention period)

Feeling feverish	Runny or stuffy nose
Headaches	Increased trouble with breathing
Cough	Fatigue (tiredness)
Sore throat or itchy/scratchy throat	Muscle or body aches
Nausea or vomiting	Diarrhea**
Rash**	Ear pain or ear discharge**

** *Only if under 18*

Exclusion criteria

Individuals meeting any of the following criteria will be excluded:

- Any serious or uncontrolled medical disorder or active infection that, in the opinion of the investigator, may increase the risk associated with study participation or study drug administration

- Inability to consent and/or comply with study protocol
- Individuals who have received oseltamivir or baloxavir within past 7 days for treatment of influenza
- Individuals with known hypersensitivity to baloxavir marboxil or oseltamivir
- Individuals with chronic kidney disease (CKD)

Withdrawal criteria

All participants are free to withdraw from the study at any time. Additionally, it is within the rights of the PI to withdraw any participant at any time during the study at her discretion.

Additional consent concerns

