Statistical analysis: Shelters will be analyzed with an intent to treat analysis to preserve the advantages of randomization. The number of influenza-positive tests will be analyzed using a generalized linear mixed model following a Poisson distribution with a log link and robust variance. The model is adjusted for calendar time and an exposure time variable based on shelter capacity. It will be used to calculate the relative risk of infection during the intervention period compared to prior to intervention, 95% confidence intervals, and p-value.

This model includes symptomatic individuals who tested throughout Year 1 of the study (November 15, 2019 – March 31, 2020).

Despite operational futility, descriptive statistics (counts, proportions, and appropriate measures of dispersion) for **both years 1 and 2** will be provided for the following Secondary Outcome Measures; additional statistical models will not be run due to low influenza case counts and the impact of the SARS-CoV-2 pandemic:

1. Feasibility of implementation of point-of-care molecular testing and treatment of influenza in shelters
 - a. Proportion of participant encounters with time between symptom onset until diagnosis with RT-PCR <48 hours in each study period
2. Feasibility of implementation of influenza treatment in shelters
 - a. Proportion of influenza-positive participants identified through on-site molecular testing in the intervention period that were treated with an antiviral
3. Proportion of participants that drop out of study
 - a. Measured as dropping out after providing consent
4. Proportion of participants that show non-compliance with study drug

- a. Only applicable to those that receive oseltamivir rather than baloxavir which is a single-dose antiviral. Measured based on self-report during follow-up visits with study research assistants.
5. Proportion of laboratory-confirmed influenza cases that report fever, or feverishness
 - a. Based on self-report, not gold standard measurement
6. Influenza viral RNA levels
 - a. Measured mean cycle threshold value for each laboratory-confirmed influenza-positive specimen collected at baseline enrollment
7. Proportion of samples with detectable influenza RNA virus at days 2/3 and days 5/6/7
 - a. Provided subject has not become lost to follow up

XI. Data Safety and Monitoring

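### The 86% power for a risk ratio of 0.50 rests on a shelter-by-month SD too small for an effect that works by blocking onward spread; at the minimum consistent clustering, power is about 70-80%

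*Combined protocol and SAP*

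**What the plan says.** Section IV (Sample size) prints power by risk ratio and number of shelter-seasons. The assumptions above the table are "Six month flu season, average shelter census = 200", "effective control incidence rate = 1.6%/month (=2%*.8" with no explanation of the factor 0.8, and "SD(shelter) = .0028, SD(shelter*month) = .0032, SD(intervention) = 0". The text then applies them: "Assuming nine shelters participating for two seasons each (18 shelter-seasons", it says, "we would have an estimated 86 percent power to detect a risk ratio of 0.50 at a 0.05 two-sided significance". Details are deferred to Additional File 2, which is not in the supplied text, and no source for the SDs is given.

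The mechanism is set out elsewhere. Section III says the strategy is evaluated "for prevention of secondary cases of influenza virus infection within homeless shelters". Section II gives the antiviral only after a positive test, and residents whose symptoms began 3-7 days earlier "will be eligible to participate in swab collection, but will not receive point-of-care testing or antiviral treatment". The outcome is not limited to secondary cases. Section X says: "The number of influenza-positive tests will be analyzed using a generalized linear mixed model following a Poisson distribution", and the measure covers all laboratory-confirmed influenza among residents.

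**The concern.** A resident who is treated has already been counted as a case. Treating that resident cannot remove the case, nor can it remove infections brought in from the community. The count can fall only through transmissions that do not happen. A large effect on the whole-shelter count therefore presupposes that many control-period cases arise from other cases in the same shelter. That is clustering, and it should appear in the shelter-by-month variance. The printed SD leaves almost no room for it.

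Every cell of the table uses the same SDs, and the 86% is the figure that the text puts forward. If it is too high, readers will overrate the trial's ability to detect a halving of influenza.

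**Working it through.** **1. Clustering implied by the printed inputs.** Mean control count per shelter-month: 200 x 0.016 = 3.2. Binomial variance: 3.2 x 0.984 = 3.15. Shelter-by-month term: (200 x 0.0032)^2 = 0.41. Variance/mean (VMR) = (3.15 + 0.41)/3.2 = 1.11. The between-shelter term adds (200 x 0.0028)^2 = 0.31 and brings the total to 1.21.

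**2. Reproducing the table.** I used a Hussey-Hughes type generalised-least-squares calculation on shelter-month proportions: fixed month effects, the two printed SDs, binomial within-cell variance with n = 200, incidence 0.016 (control) and 0.008 (intervention), and a two-sided 0.05 Wald test. The step figure is not shown, so the layout is an inference: six months, with crossovers at the start of months 2 to 5.

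| Shelter-seasons, RR 0.50 | 8 | 12 | 16 | 18 | 24 | 32 |
|---|---|---|---|---|---|---|
| Printed | 52 | 72 | 81 | 86 | 93 | 98 |
| Recomputed | 52 | 69 | 81 | 86 | 94 | 98 |

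The 12-column becomes 72 if each season's six shelters split 2/1/1/2 across the steps. For 18, a 5/4/4/5 split gives 86.1-86.7%. A five-step layout gives about 91% and does not fit.

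**3. Clustering that RR 0.50 requires.** Let introductions be Poisson with mean L per shelter-month, each starting a chain of total size S that falls within the month.

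- Mean count = L x E[S] and variance = L x E[S^2], so VMR = E[S^2]/E[S], which is at least E[S].
- In the best case every onward transmission is blocked and only introductions remain, so RR = 1/E[S].
- RR = 0.50 therefore needs E[S] of at least 2, and a control VMR of at least 2. Equality holds only if every chain is exactly a pair.
- If the factor 0.8 is case detection, thinning gives VMR = 1 + 0.8 x (2 - 1) = 1.8.
- The control-month SD that matches VMR 2 is sqrt(2 x 3.2 - 3.15)/200 = 0.0090, about 2.8 times the printed 0.0032.

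**4. Power with that clustering.** The setting is 18 shelter-seasons split 5/4/4/5, with census and incidence as printed. The binomial variance is multiplied by the VMR in control months and by 1 in intervention months. The 0.0032 term is either kept or, to avoid counting the same clustering twice, dropped.

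| Control VMR | 0.0032 kept | 0.0032 dropped |
|---|---|---|
| 1 (printed inputs) | 86.7% | not applicable |
| 1.8 (minimum, 0.8 as detection) | 74.7% | 79.2% |
| 2 (minimum) | 72.0% | 76.3% |
| 4 (Poisson branching, half of cases secondary) | 51.9% | 54.5% |

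For VMR 2 with the term kept, the standard error rises from 0.00261 to 0.00315. Then 0.008/0.00315 - 1.96 = 0.58, which gives 72%, against 0.008/0.00261 - 1.96 = 1.11, which gives 87%. Other reasonable choices of variance form and weights spread the two minimum rows over about 70-80% and the branching row over about 50-58%. Against 86%, the minimum rows lose 86 - 80 = 6 to 86 - 70 = 16 points.

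**5. Sensitivity.** A simulation that let pairs cross month boundaries, with an assumed 3-day serial interval, gave a control VMR of 2.0-2.1 and power of about 73% for a difference of 0.008. Under five steps, power falls from about 91% to about 76-82%, so the loss does not depend on the inferred layout.

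**6. Nine shelter-seasons.** Section X now limits the primary analysis to Year 1. With half the information, the printed inputs give about 57%, and minimum clustering (VMR 1.8-2) gives about 41-49%. These keep the six-month layout, although the Year 1 window (15 November to 31 March) is about four and a half months, so they are generous.

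**The case against.** The strongest reply is that nothing is miscalculated: the table reproduces, and a conflict appears only once a transmission model is added that the documents do not state. They give no secondary-case share, reproduction number or chain sizes, and Additional File 2 may explain the SDs. This stands in part. A reader might infer an arithmetic error in the table, and there is none. But the bound needs only the stated mechanism, the stated outcome and the stated RR, together with the independence assumptions listed in the verdict. An explanation of where 0.0032 came from would not change the variance it implies.

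Second, a VMR of 2 with 200 residents is an intraclass correlation of only about 1/199 = 0.005, which is not extreme, and the minimum case still leaves 70-80% power. That is right. A reader might infer that the design could not detect a halving at all; the bound does not show that. Power near 50% or below depends on chain distributions chosen for illustration.

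Third, the table openly shows limited power for smaller effects: 67% at RR 0.6, 54% at 0.65 and 41% at 0.7 for 18 shelter-seasons. True, but those cells use the same SDs.

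Fourth, Section X specifies robust variance and confidence intervals and restricts the analysis to Year 1, so the 86% may be only a planning record. Robust variance protects the inference but does not restore power. Version 2.8 still states the 86% without qualification.

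**Conclusion.** The point holds as a mismatch between the variance input and the effect being powered. At the minimum clustering consistent with RR 0.50, power for 18 shelter-seasons is about 70-80% rather than 86%, a loss of about 6-16 points. This rests on four assumptions: Poisson introductions; chains mostly within one shelter-month; a four-step layout inferred from the printed table; and, for the upper end of the range, the factor 0.8 being case detection.

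The minimum is favourable to the plan, since it takes every chain as a pair and every secondary case as averted. Residents with 3-7 days of symptoms and those who decline the intervention are not treated, so RR 0.50 would in practice need longer chains. The 50-58% for Poisson branching illustrates the direction; it is an assumption, not a finding.

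A reader might also infer that a non-significant primary result can never exclude RR 0.50. That does not follow: the reported confidence interval decides it, and a null result should be read from that interval.

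**What to change.** In Section IV and Additional File 2, recompute the power table with a control shelter-month variance that matches each risk ratio: VMR at least 1/RR, or 1 + 0.8 x (1/RR - 1) if 0.8 is detection. The minimum values are:

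| RR | 0.5 | 0.6 | 0.65 | 0.7 |
|---|---|---|---|---|
| 1/RR | 2.00 | 1.67 | 1.54 | 1.43 |
| With 0.8 as detection | 1.80 | 1.53 | 1.43 | 1.34 |

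Simulating within-shelter chains would serve equally well. State what the factor 0.8 represents, the source of the SDs, the step layout and the chain assumptions. Replace the 86% with the resulting figure, and give the corresponding figure for the nine Year 1 shelter-seasons that Section X analyses. Interpret a null primary result from its confidence interval.

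The cost is a short recalculation and some wording. Enrolment, data and the primary model are unchanged. The downside is a less favourable stated power.

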Person-to-person transmission: We will use the CDC definition for influenza transmission that refers to the ability of an influenza virus to spread from one person to another, most commonly through large or small droplets containing influenza virus that are expelled when a sick person is coughing or sneezing.

Homelessness: We will use a truncated version of the definition provided by the U.S. Department of Housing and Urban Development that identifies people who are living in a place not meant for human habitation, in emergency shelter, in transitional housing, or are exiting an institution where they temporarily resided if they were in shelter or a place not meant for human habitation before entering the institution.

X. Statistical analyses

Due to the SARS-CoV-2 pandemic onset and corresponding methodological changes, the primary outcome measure for this study will only be calculated based on data collected from Year 1. Standard surveillance beginning on March 30, 2020 expanded to include the testing of study staff and

asymptomatic individuals 3 days per week. The primary outcome measure will be calculated excluding asymptomatic individuals and shelter staff tested as part of the modified standard surveillance methodology initiated on March 30, 2020. As shelter managers were unable to provide us with reliable daily census, we were unable to establish person-days at risk for this study population. Instead, we will use unique participants as the primary unit of analysis. Overall, data collected between November 15, 2019 and March 31, 2021 will be used for data analysis.

Primary Outcome Measure

1. **Cumulative incidence** of cases of influenza (A and B) in shelters during the intervention period compared to the control period.
 - a. As daily census counts for participating shelters were not made available to the research team, person-days and therefore incidence rates will not be calculable. Cumulative incidence instead will be calculated as the number of cases of laboratory-confirmed influenza among shelter residents divided by the number of unique shelter residents tested.

Endpoint: Number of influenza-positive events in the control v. intervention periods

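### The 86% power claimed for the trial is for 18 shelter-seasons; the primary analysis now uses Year 1 only (nine), for which the plan's own table implies about 57% at RR 0.50

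*Combined protocol and SAP*

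**What the plan says.** Section IV, Sample size, prints a table of power for four risk ratios and six numbers of shelter-seasons (8, 12, 16, 18, 24, 32). From it the text adopts one figure: "Assuming nine shelters participating for two seasons each (18 shelter-seasons), we would have an estimated 86 percent power" for RR 0.50 at two-sided 0.05, with 200 participants per shelter. The table's assumptions are: "Six month flu season, average shelter census = 200, effective control incidence rate = 1.6%/month (=2%*.8", plus standard deviations of 0.0028 between shelters and 0.0032 for shelter by month. The paragraph above the table gives a different control rate: "Power calculations were based on an assumed 1.67% incidence rate per month, which was determined based on assumed 12% incidence rate" over the flu season.

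Section X changes the data set. Because of the pandemic, "the primary outcome measure for this study will only be calculated based on data collected from Year 1". The primary model is then dated: "This model includes symptomatic individuals who tested throughout Year 1 of the study (November 15, 2019 – March 31, 2020". Section X also explains: "As shelter managers were unable to provide us with reliable daily census, we were unable to establish person-days at risk". The model instead uses shelter capacity for exposure: "The model is adjusted for calendar time and an exposure time variable based on shelter capacity".

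On population size, Section II gives a maximum of 1,696 individuals under surveillance per season across the nine shelters. Section IV, explaining the expected rise in enrolment, says: "This is due to the increased target population (412 to 1,032".

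**The concern.** The claimed power and the primary analysis rest on different amounts of data. The 86% needs nine shelters in each of two seasons. The primary analysis as now written uses nine shelters in one. Section X was rewritten for the pandemic, but the power statement in Section IV was left unqualified and no power is given for the Year 1 analysis.

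What is at stake is how a non-significant primary result is read. With 86% power, such a result would be fairly strong evidence against a halving of influenza. With power in the high 50s it would not be, since a true halving would be missed in roughly four trials out of ten.

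**Working it through.** **Inputs.** Two-sided alpha 0.05 (critical value 1.96), the RR 0.50 row of the power table (52, 72, 81, 86, 93 and 98% at 8, 12, 16, 18, 24 and 32 shelter-seasons) and the table's assumptions, all from Section IV. Nine shelters, from Section II. Year 1 only, from Section X. So the primary analysis has 9 × 1 = 9 shelter-seasons, against 9 × 2 = 18.

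**Step 1: reproduce the 86%.** I used a stepped-wedge weighted-least-squares calculation on the risk-difference scale, with fixed month effects and the table's two standard deviations. It took 200 residents per shelter, a control rate of 0.016 and an effect of 0.016 × (1 − 0.50) = 0.008. Power = Φ(0.008/SE − 1.96). The readable text does not give the number of steps, so that is an assumption. Four steps over six monthly periods, with the mean rate 0.012 in the binomial variance, gives 84.9% for 18 shelter-seasons (85.7% if two separate nine-shelter seasons are combined). Other plausible schedules give 84.4–85.2%. The stated figure is sound for its condition.

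**Step 2: nine shelter-seasons from the plan's own table.** This step needs no schedule.

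- Bracket: nine lies between 52% (8) and 72% (12).
- Linear interpolation: 52 + (72 − 52)/4 = 57.0%.
- Rescaling: λ(n) = z(power) + 1.96; λ(9) = λ(n) × √(9/n); power = Φ(λ(9) − 1.96).

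| From column | λ(n) | λ(9) | Power at nine |
|---|---|---|---|
| 8 (52%) | 2.010 | 2.132 | 56.8% |
| 12 (72%) | 2.543 | 2.202 | 59.6% |
| 16 (81%) | 2.838 | 2.128 | 56.7% |
| 18 (86%) | 3.040 | 2.150 | 57.5% |
| 24 (93%) | 3.436 | 2.104 | 55.7% |
| 32 (98%) | 4.014 | 2.129 | 56.7% |

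Five of the six columns give 55.7–57.5%; only the 12 column reaches 59.6%. The four-step model of Step 1 gives 57.1% directly. A five-step version, with the control rate in the variance, gives 53.1%.

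**Step 3: smaller effects**, rescaled from the 8, 12 and 18 columns.

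| RR | Table at 18 | At nine |
|---|---|---|
| 0.60 | 67% | 37.5, 40.5, 39.6% |
| 0.65 | 54% | 29.8, 31.5, 30.7% |
| 0.70 | 41% | 23.1, 24.4, 23.1% |

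**Step 4: are the table's assumptions generous for Year 1?** From 15 November 2019 to 31 March 2020 inclusive is 16 + 31 + 31 + 29 + 31 = 138 days, about 4.5 months against the assumed six. A census of 200 in nine shelters is 1,800 people. The stated maximum gives 1,696/9 = 188 per shelter, and the target population gives 1,032/9 = 115. Both departures lower power.

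**Step 5: inputs that disagree.** 12%/6 = 2.0% per month, and 2.0% × 0.8 = 1.6%, which is the table's rate. The text's 1.67% × 6 = 10%, not 12%. In the four-step model, power at nine is 57.1% with 1.6% and 59.3% with 1.67%, so this discrepancy is worth only about 2 points. Separately, 1,800 exceeds the stated maximum of 1,696.

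**The case against.** The strongest reply is that nothing was miscalculated. The 86% is explicitly conditional on two seasons, it reproduces, and the pandemic forced the change. That stands: this is a design figure left unlabelled, not a wrong sum. It is also untrue that 86% is the only power printed. The table shows 24 values, including the two that bracket nine. It is, however, the only one the text claims for the trial.

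A second reply is that Section X is already candid about operational futility, low case counts and the lack of a census. The futility and low-count remarks, though, introduce the secondary outcomes and explain why no further models will be run for those. The primary test still goes ahead with a p-value, and no power is given for it.

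A third is that power worked out after data collection is pointless because the confidence interval shows precision. Section X does already require a relative risk with a 95% interval, so a further sentence on reading a null result would be a matter of preference, and none is asked for here. But restating the planned calculation at the planned RR, for the data set now specified, is not observed-effect power.

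Finally, Additional File 2, cited for the power details, is not in the readable text. It may hold the step schedule or explain the two control rates. It would not change the unqualified statement in Section IV.

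**Conclusion.** The point holds. The power claimed in Section IV does not apply to the primary analysis in Section X. On the table's own assumptions, nine shelter-seasons give about 57% power for RR 0.50 (56–60% by method), roughly 29 points below the 86% claimed. For RR 0.60, 0.65 and 0.70 the figures are about 38–41%, 30–32% and 23–24%. The 18-versus-nine mismatch and the 52–72% bracket come straight from the documents. The 57% assumes only that the table's information scales with the number of shelter-seasons.

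It is likely an upper value, given the shorter window and the smaller shelters. A reader might go further and infer that true power was near 40%. The four-step model does give 40% at 115 per shelter, but that takes the lowest of the population figures and an assumed step schedule, and the target population is not defined as a nightly census. At 188 per shelter the same model gives 55%. The documents do not settle which applies. Nor do they show which control rate or census is right.

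**What to change.** In Section IV, keep the 86% but label it as the design figure for two seasons (18 shelter-seasons). Add that the Year 1 primary analysis, with nine shelter-seasons, has about 57% power for RR 0.50 on the table's assumptions. The sponsor should confirm that figure with the planned step schedule and the 15 November 2019 to 31 March 2020 window.

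In the same section, reconcile the control rate (1.67% per month in the text, 1.6% in the table) and the census of 200 per shelter (1,800 in all, against a stated maximum of 1,696), without presuming which value is right.

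The cost is a label, one added figure, one recalculation and two reconciled inputs. No participants or data are added. This version is dated March 2022, after data collection, so conduct cannot change. The only price is a less favourable stated power.
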